All patients randomized and who received any part of at least one infusion of randomized treatment will be evaluated for safety according to the treatment actually received. The safety analyses will include evaluation of the incidence of treatment-emergent AEs, SAEs, and AEs leading to discontinuation of study treatment tabulated by Overall, System Organ Class, and Preferred Term using the MedDRA coding system. Additional tables with AEs by severity and relationship to drug as assessed by the PI will be presented. Laboratory data, vital signs, radiologic evidence, drug and cytokine concentrations, and ECGs assessments will be evaluated over time on study using descriptive statistics, including changes from baseline. Shift analyses of relevant clinical laboratory parameters will be produced showing shifts across low, normal, and high categories.

DOCUMENT APPROVAL

This study will be conducted in compliance with the protocol, Good Clinical Practice (GCP) and applicable regulatory requirements.

ARCH BIOPARTNERS REPRESENTATIVE

Signature

[name]

Date 17-March-2021

PRINCIPAL INVESTIGATOR

Signature

Print Name: [name]

18-March-2021

Date

TABLE OF CONTENTS

SYNOPSIS.....	2
1 LIST OF ABBREVIATIONS.....	14
2 ETHICAL CONDUCT OF THE STUDY AND REGULATORY REQUIREMENTS	17
2.1 Institutional Review Board (IRB) or Ethics Committee (EC).....	17
2.2 Ethical Conduct of the Study	17
2.3 Patient Information and Consent	17
3 INTRODUCTION	18
3.1 COVID-19 Background.....	18
3.2 Acute Respiratory Distress Syndrome.....	19
3.2.1 Scoring systems	24
3.3 LSALT peptide	25
3.3.1 Inflammation and Organ Injury	25
3.3.2 Pre-Clinical Data for Dipeptidase-I and LSALT Peptide in AKI	27
3.3.3 Drug Metabolism and Pharmacokinetics.....	29
3.3.4 Toxicology and Safety.....	29
3.3.5 Preliminary Safety in Humans.....	31
3.3.6 Pharmacokinetics	32
3.4 Study Rationale.....	32
3.5 Dose Justification.....	33
4 STUDY OBJECTIVES AND ENDPOINTS.....	34
4.1 Study Objectives.....	34
4.1.1 Primary Objective	34
4.1.2 Secondary Objectives	34
4.1.3 Health Outcomes Objective.....	35
4.1.4 Exploratory Objectives	35
4.2 Study Endpoints.....	35
4.2.1 Primary Efficacy Endpoint	35
4.2.2 Secondary Efficacy Endpoints.....	35
4.2.3 Health Outcomes endpoint:	36
4.2.4 Exploratory Endpoints:.....	36
4.2.5 Safety Endpoints.....	36
5 INVESTIGATIONAL PLAN.....	36
5.1 Overall Study Design and Plan – Description	36
5.2 Number of Patients (Planned).....	37
5.3 Discussion of Study Design.....	38

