7.3.1 Adverse Events

An adverse event (AE) is any untoward medical occurrence in a patient participating in a clinical trial. An AE can be any unfavorable and unintended sign, symptom, or disease temporally associated with the use of the study medication, whether or not considered related to the study medication. AEs will be collected from the initiation of treatment until 30 days following the final dose. Pre-existing known clinically significant conditions observed at screening should be recorded as medical history.

This definition also includes accidental injuries, reasons for any change in medication (drug and/or dose), reasons for re-admission to a hospital, or reasons for surgical procedures (unless for minor elective surgery for a pre-existing condition). It also includes adverse events commonly observed and adverse events anticipated based on the pharmacological effect of the study medication. Any laboratory abnormality assessed as clinically significant by the PI must be recorded as an adverse event.

A treatment-emergent adverse event (TEAE) is also defined as any adverse event occurring after start of study medication and within the time of residual drug effect (30 days after the last administration of the study medication), or a pre-treatment adverse event or pre-existing medical condition that worsens in intensity after start of study medication and within the time of residual drug effect.

Adverse events should be recorded as diagnoses, if available. If not, separate sign(s) and symptom(s) are recorded. One diagnosis/symptom should be entered per record.

Note that death is not an adverse event but the cause of death is. An exception is the adverse event of sudden death of unknown cause. Note that hospitalization is not an adverse event; however, the reason for hospitalization is. Procedures are not adverse events; the reasons for conducting the procedures are. In general, only the reason for conducting the procedure will be captured as an adverse event. However, if deemed necessary by the PI, a procedure can be captured along with the reason for conducting the procedure.

An overdose or medication error is not an adverse event unless it is temporally associated with an unfavorable or unintended sign or symptom.

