7.3.1.1 Serious Adverse Events

Each AE is to be classified by the PI as serious or non-serious. A serious adverse event (SAE) is any untoward medical occurrence or effect that occurs at any dose:

- Results in death
- Is life-threatening (*i.e.*, an immediate risk of death)
- Requires in-patient hospitalization or prolongation of existing hospitalization
- Results in persistent or significant disability/incapacity
- Is associated with a congenital anomaly/birth defect
- Is an important medical event.

An adverse event caused by an overdose or medication error is considered serious if a criterion listed in the definition above is fulfilled.

Important adverse events that may not result in death, may not be life-threatening, or do not require hospitalization may be considered serious when, based upon appropriate medical judgment, they may jeopardize the patient's safety or may require medical or surgical intervention to prevent one of the outcomes listed above.

Serious adverse events also include any other event that the PI or Sponsor judges to be serious or which is defined as serious by the regulatory agency.

The PI is to report all directly observed adverse events and all adverse events spontaneously reported by the trial patient using concise medical terminology.

7.3.1.2 Procedures for Assessing, Recording, and Reporting Adverse Events and Serious Adverse Events

Throughout the duration of the study, the PI will closely monitor each patient for evidence of drug intolerance and for the development of clinical or laboratory evidence of adverse events. All AEs (expected or unexpected) which occur during the course of the study, whether observed by the PI or by the patient, and whether or not thought to be drug-related, will be reported and followed until resolution or until they become stable.

The description of the AE will include description of the event, start date, stop date, intensity, if it was serious, relationship to test drug, change in test drug dosage, if the patient died, and if treatment was required. Events will be recorded as one of the following severity/causality categories below (CTCAE v5.0):

Severity	Definition
Mild (Grade 1)	Asymptomatic or mild symptoms, clinical or diagnostic observations only; intervention not indicated
Moderate (Grade 2)	Minimal, local or noninvasive intervention indicated; limiting age-appropriate instrumental ADL (e.g., meal preparation, shopping, using telephone, managing money, etc.)

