9.3.6 Study Stopping Rules

The progress of the study will be monitored by the DSMB on an ongoing basis according to the DSMB Charter with meetings at monthly intervals or more frequently dependent upon the rate of enrollment. These meetings will include an assessment of differences in the number of subjects with an unfavorable outcome for the primary endpoint, as well as observed imbalances in severity or risk factors and the totality of data, including adverse event profiles not associated with an unfavorable primary endpoint value. Consideration will also be given to the limited information available in the early stages of the study and a potential for unfavorable trends with very few subjects due to chance alone.

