9.3.6.1 Safety Indices

- The observed adverse event profile of the patients on the treatment arm exceeding the incidence and/or severity of adverse events observed in the placebo arm to a significant degree at any time during the study.
- Primary endpoint: there will be no more than a 1-subject difference in the number of subjects with an unfavorable outcome for the primary endpoint after the first 6 subjects completed active treatment compared with placebo (in favor of placebo). Subsequently, for the total number of 18 subjects, there will be no more than a 2-subject difference in the primary endpoint (in favor of placebo) and no more than a 3-subject difference for the remaining subjects. Otherwise, the DSMB will consider stopping the study for safety reasons.

For the primary endpoint, each of these scenarios is considered unlikely in the presence of at least a modest relative reduction in the incidence rate of only 20 percent (*i.e.*, a rate of 22.4% for LSALT from an assumed incidence rate of 28% for placebo), with probabilities in the range of 6% or less for these unfavorable outcomes at the end of each cohort, under this assumption.

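### The overall TEAE and SAE rows include efficacy-endpoint events, so a drug benefit offsets drug-caused SAEs there; a second set of rows without those events is a cheap improvement

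*Combined protocol and SAP*

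**What the plan says.** The synopsis, under Safety Analysis, states: "The safety analyses will include evaluation of the incidence of treatment-emergent AEs, SAEs, and AEs leading to discontinuation of study treatment tabulated by Overall". The sentence goes on to SOC and PT, and the next one adds tables by severity and by investigator-assessed relationship. Section 9.3.4.1 summarises by arm the incidence of specific AEs, of AEs causing withdrawal and of SAEs, gives severity and attribution within body system, and plans narratives for serious or otherwise significant events.

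The definitions are broad. Section 7.3.1 says "An AE can be any unfavorable and unintended sign, symptom, or disease temporally associated with the use of the study medication", related or not. It treats the cause of a death as an AE and collects events until 30 days after the last dose, which covers Day 28. Section 7.3.1.1 makes an event serious if it is fatal, life-threatening, or "Requires in-patient hospitalization or prolongation of existing hospitalization". Neither section exempts the failures that make up the primary endpoint.

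For monitoring, section 9.3.6 has the DSMB look at unfavourable primary outcomes and also at "adverse event profiles not associated with an unfavorable primary endpoint value". The first index in 9.3.6.1 is the LSALT adverse event profile "exceeding the incidence and/or severity of adverse events observed in the placebo arm to a significant degree". It does not mention that separation.

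**The concern.** The trial is meant to prevent ARDS and AKI in hospitalised patients. Respiratory failure, dialysis and death from COVID-19 are therefore efficacy outcomes and, under these definitions, also adverse events, most of them serious. An overall SAE row then carries benefit and harm in one number. If LSALT prevents some disease events, its SAE count falls, and SAEs that it causes can bring the count back up to the placebo level. The two arms would look alike in that row although the drug had caused harm.

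This matters because section 9.1 gives the wish to assess safety as a reason for choosing 60 patients. Section 9.3.6 shows that the protocol already recognises the distinction; what is missing is its use in the AE index and in the final tables.

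**Working it through.** **Inputs.** Section 9.3.6.1 gives "a rate of 22.4% for LSALT from an assumed incidence rate of 28% for placebo", described as "at least a modest relative reduction in the incidence rate of only 20 percent": 0.28 × 0.8 = 0.224. Section 9.1 gives 30 patients per arm. The documents give no SAE rates. Three quantities are therefore assumptions: the share f of endpoint failures recorded as SAEs, the drug-caused SAE rate h, and the background rate b of other SAEs.

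**The plan's own figure.** Section 9.3.6.1 describes its primary-endpoint limits as crossed "with probabilities in the range of 6% or less for these unfavorable outcomes at the end of each cohort". Exact binomial tails for LSALT minus placebo, reading 6, 18 and 60 as total subjects, are:
- 3 per arm, difference above 1: 5.3%
- 9 per arm, difference above 2: 4.9%
- 30 per arm, difference above 3: 6.1%

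This reproduces the statement and confirms how the two rates are used: they are rates of unfavourable Day 28 status.

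**Break-even harm, independent of endpoint failure.** Overall SAE rates are 0.28f on placebo and 1 − (1 − 0.224f)(1 − h) on LSALT. They are equal at h = 1 − (1 − 0.28f)/(1 − 0.224f).

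| f | Calculation | Break-even h |
|---|---|---|
| 100% | 1 − 0.720/0.776 | 7.2% |
| 75% | 1 − 0.790/0.832 | 5.0% |
| 50% | 1 − 0.860/0.888 | 3.2% |
| 25% | 1 − 0.930/0.944 | 1.5% |

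At f = 100%, both arms expect 30 × 0.28 = 8.4 patients with an SAE. An independent background multiplies both SAE-free proportions by (1 − b), so it cancels and break-even does not change.

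**Harm only in patients without an endpoint event (f = 100%).** Break-even is 0.28 − 0.224 = 5.6%.

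**With endpoint events shown apart.** The expected excess is h(1 − b). At h = 7.2% this is 7.2 points with no background (30 × 0.072 = 2.2 patients against 0), 6.9 points at b = 5% and 6.5 points at b = 10%.

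**What 30 per arm can show.** Exact calculation at h = 7.2%, f = 100%. The Fisher column is the chance of a two-sided p < 0.05 with LSALT higher.

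| Presentation | LSALT count higher at all | Fisher |
|---|---|---|
| Pooled, b = 0 | 44% | 1.3% |
| Separated, b = 0 | 89% | 1.9% |
| Separated, b = 5% | 77% | 3.8% |
| Separated, b = 10% | 71% | 4.4% |

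The middle column must be read against its value when the drug causes no harm. The separated row then still shows LSALT higher 38% of the time at b = 5% and 41% at b = 10%. The pooled row under the assumed benefit does so 26% of the time.

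**The case against.** The overall row is not the only view. Respiratory failure and AKI code to their own terms, so the SOC and PT tables already allow a reader to set them apart, and the relationship tables and narratives offer another route. Section 9.3.4.1 defines incidence for a specific AE and does not itself call for an overall TEAE line. The index in 9.3.6.1 sits under 9.3.6, so a DSMB may well apply the separation stated there. The separate SAP and the DSMB Charter are not in the supplied text, and part of the AE reporting section is not available, so an exemption or an extra table could exist in any of them. All-event reporting is also conventional, and nothing in it is wrong.

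Most of this stands and limits the point. What remains is that the by-term and relationship tables help only in part. About two patients in 30 spread over several terms would not stand out, and relationship rests on investigator judgement, with events judged possibly related counted as related (section 7.3.1.2).

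A reader might infer that the plan would conceal a drug harming 7% of patients, or that separation raises detection from 44% to 89%. The documents support neither. The 7.2% is the top of the range calculated here and rests on two unstated assumptions. The 89% counts one patient against none as detection and, with no background, is simply the chance of at least one drug-caused SAE in 30 patients.

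**Conclusion.** The point holds as a cheap improvement to the safety presentation, not as an error that hides toxicity. In the supplied text, the overall TEAE and SAE rows include efficacy-endpoint events, and the split named in 9.3.6 is not repeated in the AE index or the final tables. In expectation, any benefit on those events offsets drug-caused SAEs in the overall row.

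The size is a scenario. Break-even harm is 7.2% if every Day 28 failure is an SAE and harm is independent of it, 5.6% if harm falls only on patients without an endpoint event, and 5.0%, 3.2% or 1.5% if 75%, 50% or 25% of failures are recorded as SAEs. Day 28 status also misses respiratory failure that resolved earlier, so the true share of endpoint events in the SAE row is unknown. The figures concern SAEs only; the documents give no rates from which to do the same for TEAEs.

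At 7.2% harm, formal detection is about 1% pooled and 2% to 4% separated. Sample size is the main limit either way. The gain is a descriptive SAE difference that benefit does not offset.

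**What to change.** In the synopsis Safety Analysis and in 9.3.4.1, pre-list the endpoint and disease-progression terms while still blinded: ARDS or respiratory failure, ventilation or ECMO, AKI or renal replacement therapy, COVID-19 worsening, and deaths from these. Show the Overall and SOC rows for TEAEs, SAEs and AEs leading to discontinuation twice, with and without the listed terms, and keep the all-event version. State in 9.3.6.1 that the AE index is reviewed in both versions, in line with 9.3.6. If the SAP or the DSMB Charter already provides this, a cross-reference is enough. Reporting of individual SAEs does not change.

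The cost is one term list and a few more tables. The version without endpoint events must not be read alone, because drug-caused lung or kidney harm would be left out of it.

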4.1.2 Secondary Objectives

To evaluate the following:

- Incidence and time to mild, moderate, and severe ARDS between treatment groups
- Ventilation-free days
- Time on nasal canula or oxygen mask
- 28-day mortality— both all-cause and attributable
- ICU length of stay (in days)
- Hospitalization length of stay (in days)
- Virologic clearance rate
- Incidence of other organ disorders
- Need and duration for extracorporeal membrane oxygenation (ECMO)
- Vasopressor-free days
- Clinical improvement in chest x-rays
- Change in baseline modified Medical Research Council (mMRC) dyspnea scale
- SOFA scores assessed periodically
- Change from baseline in liver function tests (ALT, AST, and/or total bilirubin)
- Change from baseline in SCr and eGFR

¹ eGFR is calculated from the serum creatinine according to the eGFR_{CKD-EPI} equation (Levey *et al*, 2009):
$$\text{eGFR (mL/min/1.73 m}^2\text{)} = 141 \times \min(S_{\text{cr}}/\kappa, 1) \alpha \times \max(S_{\text{cr}}/\kappa, 1) - 1.209 \times 0.993 \text{Age} \times 1.018 \text{ [if female]} * 1.159 \text{ [if black], where } S_{\text{cr}} = \text{serum creatinine; } \kappa = 0.7 \text{ for females and } 0.9 \text{ for males; } \alpha = -0.329 \text{ for females and } -0.411 \text{ for males; min indicates the minimum of } S_{\text{cr}}/\kappa \text{ or } 1, \text{ and max indicates the maximum of } S_{\text{cr}}/\kappa \text{ or } 1.$$

- Change from baseline in highly-sensitive troponin (hs-troponin)
- Change from baseline ACT, aPTT, and/or PT/INR levels
- Change from baseline for antiviral immunoglobulins (IgG, IgM, and IgA) at EOS.

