5.4 Selection of Study Population

5.4.1 Inclusion Criteria

Eligible patients must fulfill the following inclusion criteria:

1. Male or female hospitalized patients between 18 and 80 years of age at time of consent.
2. Clinical and laboratory diagnosis of COVID-19 infection. Patients must be positive for the SARS-CoV-2 by Real-Time Reverse Transcriptase (RT)-PCR Diagnostic Panel or have an existing complication secondary to SARS-CoV-2 infection which was positive within 2 weeks of entry into the study. Further, patients must have at least two of the following three symptoms:
 - Fever (oral temperature $\geq 100.4^{\circ}\text{F}$ [$> 38^{\circ}\text{C}$]) with or without chills
 - Dyspnea or difficulty breathing (≥ 2 on mMRC dyspnea scale)
 - Nonproductive cough (Stokes *et al*, 2020),
 - Or other signs and symptoms of established complications to SARS-CoV-2 infection (*e.g.*, coagulopathy, cardiomyopathy, acute kidney injury [AKI], and/or acute liver injury) within the limits of Exclusion Criteria #8.
3. Patients must present with moderate to severe illness as defined below:
 - Moderate illness: Patients who have evidence of lower respiratory disease by clinical assessment or imaging and an oxygen saturation (SpO_2) $> 93\%$ on room air at sea level
 - Severe illness: Patients who have a respiratory frequency > 30 breaths per minute (bpm), $\text{SpO}_2 \leq 93\%$ on room air at sea level, ratio of arterial partial pressure of oxygen to fraction of inspired oxygen ($\text{PaO}_2/\text{FiO}_2$) < 300 , or lung infiltrates $> 50\%$ (COVID-19 Treatment Guidelines Panel, 2020).
4. APACHE II score < 20 or establishment of survivability of the patient beyond 48 hours

following randomization.

5. Therapies which have been shown to be beneficial and are included in standard-of-care COVID-19 treatment guidelines (e.g., those of WHO or NIH, or institutional guidelines) are permitted.

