5.4.2 Exclusion Criteria

The presence of any of the following excludes a patient from study enrollment:

1. Known sensitivity, allergy, or previous exposure to LSALT peptide.
2. Exposure to any investigational drug or device <90 days prior to entry into study.
3. Treatment with immunomodulators or immunosuppressant drugs, including but not limited to IL-6 inhibitors, TNF inhibitors, anti-IL-1 immunomodulators, and JAK inhibitors within five half-lives or 30 days (whichever is longer) prior to randomization and throughout the study period. However, should any of these treatments become SOC and incorporated into clinical treatment guidelines (e.g., those of WHO or NIH, or institutional guidelines), the treatment is permitted. Further, low-dose oral prednisone (≤ 20 mg/day) and inhaled steroids (e.g., for treatment of asthma) are allowed in the study.
4. Anticipated transfer to another hospital or medical center within 72 hours, which is not a study site.
5. Uncontrolled or poorly-treated active hepatitis B (HBV), hepatitis C (HepC), or HIV infection. Those subjects who are positive for HBV, HepC, or HIV but are well-controlled with low viral loads are allowed to participate in the study:
 - HBV low viral load defined as $<20,000$ IU/mL
 - HepC low viral load defined as $<800,000$ IU/mL
 - HIV low viral load defined as <5000 copies/mL.
6. Participation in another drug or device study at any time during this study, for example:
 - Ulinastatin 200,000 IU or greater (ClinicalTrials.org NCT03089957)
 - High dose intravenous Vitamin C (ClinicalTrials.org NCT042645333)

- Budesonide and formoterol (Festic *et al*, 2017)
- Bevacizumab to prevent ARDS (NCT01314066)
- Dornase alfa to reduce hypoxemia in ventilated trauma patients (Pottecher *et al*, 2020).

7. As indicated in the inclusion criteria, pregnant female patients are excluded from study. Further, female patients who are nursing are excluded from study.

8. Has any medical condition considered to be clinically significant and could potentially affect patient safety or study outcome, including but not limited to:

- Acute kidney injury (Thomas *et al*, 2015) or chronic kidney disease (stage-4 and stage-5 renal impairment [Wongrakpanich *et al*, 2017; Agarwal, 2016]; hemodialysis or eGFR < 30 mL/min/1.73 m²; [CKD-EPI equation; Levey *et al*, 2009])
- End-stage malignancy undergoing treatment

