- Immunocompromised patients or those with medical/surgical conditions (*e.g.*, solid organ transplantation) which require chronic immunosuppression
- Chronic hematologic disease which, in the opinion of the PI, prohibits the patient from entering into study
- Acute liver injury with AST and/or ALT levels greater than 3x ULN, unless recent injury (within 2 weeks) likely due to COVID-19 infection
- History of coagulopathy of unknown etiology, as defined by abnormal ACT (only if part of SOC), aPTT, and/or PT/INR values at least 2-fold outside normal limits, and currently present at screening, and/or
- End-stage lung disease, acute lung injury, very severe chronic obstructive pulmonary disease (COPD) as assessed by the GOLD criteria (GOLD Stage IV; Vogelmeier *et al*, 2017), or mechanical ventilation.

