7 EFFICACY AND SAFETY ASSESSMENTS

7.1 Efficacy Assessments

7.1.1 Primary Efficacy Endpoint

The primary efficacy endpoint is the proportion of subjects alive and free of respiratory failure (*e.g.*, need for non-invasive or invasive mechanical ventilation, high flow oxygen [≥ 6 L/minute], or ECMO) and free of the need for continued renal replacement therapy (RRT) on Day 28. The need for continued RRT at Day 28 will be defined as either dialysis in the past 3 days (Day 26, 27, or 28) or an eGFR on Day 28 <10 mL/min/1.73 m².

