9.3.4.2 Clinical Laboratory

Clinical Laboratory examination will be performed prior to treatment and during treatment.

Descriptive statistics will be presented for the observed values and change from baseline of each of the clinical laboratory results by treatment and visit. Shift tables describing abnormality shifts from baseline to after treatment and follow-up (Day 28) will be created.

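### Laboratory shift tables by low/normal/high cannot show worsening in patients who enter with already abnormal liver, kidney or clotting values

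*Combined protocol and SAP*

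**What the plan says.** **Shift tables.** The synopsis (Safety Analysis) states: "Shift analyses of relevant clinical laboratory parameters will be produced showing shifts across low, normal, and high categories". Section 9.3.4.2 states: "Shift tables describing abnormality shifts from baseline to after treatment and follow-up (Day 28) will be created". The second sentence names two comparison points but no categories, toxicity grades or rule for choosing among several post-baseline values. No other section plans a graded laboratory shift table.

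**Who can enter.** Exclusion criterion 8 (section 5.4.2) sets these limits:

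- Liver: excluded for "Acute liver injury with AST and/or ALT levels greater than 3x ULN, unless recent injury (within 2 weeks) likely due to COVID-19 infection". Values up to 3 times ULN are therefore admitted, and higher values without a stated ceiling if the injury is recent and attributed to COVID-19.
- Kidney: excluded for "hemodialysis or eGFR < 30 mL/min/1.73 m²", so an eGFR of 30 or more can enter.
- Clotting: excluded for a history of coagulopathy of unknown cause with "aPTT, and/or PT/INR values at least 2-fold outside normal limits". Smaller deviations, or those with a known cause, can enter.

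Inclusion criterion 2 (section 5.4.1) also counts established complications toward eligibility: "coagulopathy, cardiomyopathy, acute kidney injury [AKI], and/or acute liver injury) within the limits of Exclusion Criteria #8".

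**The concern.** A three-level table has a ceiling. A patient whose ALT stays at 2 times ULN and one whose ALT rises from 2 to 12 times ULN fall in the same cell, high to high. A patient who moves from just below to just above the ULN is counted as a shift. For anyone who starts above the ULN, the table has no cell in which an upward change can appear. For eGFR the same happens at the low end.

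Eligibility here makes such starting values possible by design. Clinical laboratory tests are a named safety endpoint (section 4.2.5), and section 9.1 gives the assessment of safety as one ground for the sample size. With 30 patients per arm, a handful of patients with marked organ worsening would matter, and the shift table is where a reader looks for the count of patients who worsened and from what level.

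**Working it through.** There is no stated figure to reproduce. The check is whether values that the protocol admits, followed by a clinically large worsening, stay in one category.

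**Kidney, from the protocol's own figures.** Inputs:

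- The equation in the footnote to section 4.1.2: "eGFR is calculated from the serum creatinine according to the eGFR_{CKD-EPI} equation".
- The entry limit, eGFR 30 (section 5.4.2).
- The renal threshold in the primary endpoint (section 7.1.1): "eGFR on Day 28 <10 mL/min/1.73 m²".
- Assumption: ULN for creatinine of 1.2 to 1.4 mg/dL. The protocol gives no reference range. For orientation, creatinine starts to score at 1.2 mg/dL in the SOFA table (Appendix 4) and above 1.4 mg/dL in the APACHE II table (Appendix 6).

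For creatinine above κ (0.9 for men, 0.7 for women), and without the race term, the equation inverts to

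creatinine = κ × [141 × 0.993^age × (1.018 if female) / eGFR]^(1/1.209).

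Man aged 60: 141 × 0.993^60 = 92.5.

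- eGFR 30: 0.9 × (92.5/30)^(1/1.209) = 2.28 mg/dL
- eGFR 10: 0.9 × (92.5/10)^(1/1.209) = 5.67 mg/dL
- Ratio: 3^(1/1.209) = 2.48, whatever the age and sex

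Both values exceed the assumed ULN, so the table shows high to high. The extremes over the eligible age range are:

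| Patient | Creatinine at eGFR 30 (mg/dL) | Creatinine at eGFR 10 (mg/dL) |
|---|---|---|
| Man, 18 | 2.92 | 7.23 |
| Woman, 80 | 1.61 | 3.98 |

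For a patient at the entry limit, the result holds for any ULN below 1.61 mg/dL. It does not hold for every patient with reduced eGFR. A 60-year-old man at eGFR 60 has creatinine 1.29 mg/dL, which is high at a ULN of 1.2 and normal at 1.4. The ceiling applies only where the baseline value is already outside the range.

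If eGFR itself is tabulated, 30 to 10 is low to low under any lower limit above 30.

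**Liver and clotting, illustrative values (assumed).**

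| Test | Baseline (× upper limit) | Later (× upper limit) | Fold rise | Shift shown |
|---|---|---|---|---|
| ALT | 2 | 12 | 12/2 = 6 | high to high |
| ALT, recent COVID-related injury | 3.1 | 20 | 20/3.1 = 6.5 | high to high |
| INR | 1.9 | 4 | 4/1.9 = 2.1 | high to high |

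The first two baselines are allowed by the liver criterion (the second through its exception), and the third lies under the 2-fold clotting limit.

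**What the other planned outputs show.**

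| Output | Where | What it captures | What it leaves out |
|---|---|---|---|
| Observed values and change from baseline, with minimum and maximum | 9.3, 9.3.4.2 | That an extreme value or change occurred | How many patients worsened, and from what baseline |
| Change in ALT, AST, bilirubin, creatinine, eGFR and clotting as secondary endpoints, by MMRM or ANCOVA | 7.1.2, 9.3.2 | Between-arm difference with no category ceiling | A per-patient count |
| SOFA, 0 to 4 | Appendix 4 | Graded bilirubin, creatinine and platelets | ALT, AST, INR, aPTT |
| Adverse events with worst severity per patient, including baseline events that worsen | 7.3.1, 9.3.4.1 | Per-patient worst severity | Abnormalities that the investigator does not judge clinically significant |

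**The case against.** The strongest reply is that the plan already sees this worsening elsewhere, and much of that stands. In the renal example, creatinine from 2.28 to 5.67 mg/dL moves the SOFA renal score from 2 to 4, and an eGFR below 10 on Day 28 is a failure of the primary endpoint. An ALT of 12 times ULN at a visit would show in the maximum and would probably be reported as an adverse event. It would therefore be wrong to infer that the safety analysis is blind to organ worsening. What remains is ALT/AST and clotting: SOFA does not score them, the summaries and models are group-level, and the adverse-event route depends on the investigator's judgement. The severity definitions in section 7.3.1.2 are general descriptors without laboratory cut-offs.

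A second reply is that section 9.3.4.2 names no categories and section 9.3 defers detail to a separate SAP, which could add grades. That is fair, but no such text is in the document reviewed, and the only categories stated are the three in the synopsis.

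Two stronger readings are tempting and are not supported:

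- A reader might infer that a large share of patients starts at the ceiling. The documents give no baseline distribution for any laboratory test, so no number or percentage can be stated.
- A reader might infer that peaks in samples drawn when clinically indicated will be missed. The plan collects these samples and does not exclude them from the tables; it is silent on the matter.

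On the kidney, section 5.4.2 can also be read as excluding all acute kidney injury, although section 5.4.1 lists it as a qualifying complication. Under either reading, chronic disease with an eGFR of 30 or more can enter, so the point does not depend on which is meant.

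**Conclusion.** The point holds as a limit of the shift tables only. As stated, they cannot register worsening in a patient whose baseline value is already outside the normal range in the same direction, and the entry criteria admit such patients for liver, kidney and clotting tests. For an individual, the unseen change can be large: a 2.48-fold rise in creatinine from the entry limit to the eGFR 10 threshold follows from the protocol's equation, given a ULN below the baseline value. The 6-fold ALT and 2.1-fold INR examples rest on assumed follow-up values. How many patients this touches is unknown.

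The practical gap is the lack of an objective per-patient count of worsening for ALT/AST and clotting. Bilirubin and creatinine are partly covered by SOFA. The primary analysis is not affected. This is a modest but cheap improvement to safety reporting.

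**What to change.** Amend the synopsis (Safety Analysis) and section 9.3.4.2, and carry the detail into the SAP before database lock:

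- For ALT, AST, bilirubin, creatinine/eGFR and INR/aPTT, tabulate baseline category against worst post-baseline category to Day 28, by treatment.
- Define categories by CTCAE v5.0 grade, the scale that the protocol already cites for adverse events and treatment discontinuation, or by multiples of ULN, and of baseline where the baseline is abnormal. Write the cut-offs into the SAP, because the protocol does not reproduce them.
- State that all post-baseline samples count, including those drawn when clinically indicated.
- Keep low/normal/high for the other tests.

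The tests are already collected, so the cost is extra table programming. One drawback needs stating with the tables: a worst-value summary depends on how often patients are sampled, so uneven unscheduled sampling between arms can influence it. Retaining the planned by-visit summaries alongside gives the reader a check.
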